APPENDIX I – EORTC QLQ - LC13 Quality of Life Questionnaire (Lung Cancer)

APPENDIX II – Common Terminology Criteria for Adverse Events (CTCAE) version 4.0

1.0 Study Schema

This trial is a seamless phase I/II prospective, single arm, cohort study.

Phase I of the trial will consist of two patients and will serve to conduct quality assurance assessments and to familiarize thoracic surgeons, radiation oncologists, and medical physicists at CancerCare Manitoba and Health Sciences Center in the use and work flow of the Health Canada approved endobronchial implanted real-time tumor tracking transponder beacons (The Calypso™ beacon). Patients in phase I will undergo standard stereotactic ablative radiotherapy (SABR) of a lung tumor with prior endobronchial transponder beacon placement. For phase I, the transponder beacons will be used for comparative localization analyses and SABR treatment setup procedures will be carried out independent of transponder beacon data, however, transponder data will be collected in order to conduct, post-treatment, *in vivo* quality assurance assessments of beacon performance characteristics. Otherwise, the SABR treatment for phase I will consist of the currently accepted standard internal target volume based and standard image guided SABR.

Phase II of this trial will consist of 26 patients who will undergo a specialized form of SABR radiotherapy specifically designed to take full advantage of the real-time tumor tracking ability of the Calypso™ transponder beacons. Specifically, SABR in phase II will consist of smaller radiotherapy treatment volumes employing respiratory gating and smaller planning target volume expansion margins given the superior tumor location telemetry afforded by the Calypso™ beacons. Comparative dosimetric analyses contrasting the traditional ITV/PTV style treatments to those with reduced ITV/PTV margins achieved via Calypso guided SABR will be performed. Patient self-reported quality of life and toxicity assessments will be collected with the goal of facilitating power and sample size calculations for the design of a larger phase III randomized controlled trial of Calypso guided SABR treatment in the future.

Phase I (n=2)

Adults ≥ 18 years of age
T1N0M0 or T2N0M0 (<4cm) NSCLC; or
A single Metastatic Lung Tumor < 4cm
ECOG performance status 0 to 2
Surgically inoperable
Non-Oxygen dependent at baseline

“Standard” Stereotactic Ablative Radiotherapy:

- 1) Endobronchial Calypso Beacon Placement
- 2) 4-Dimensional CT Simulation Scan
- 3) ITV based “standard” SABR planning with 5mm PTV Expansion margins
- 4) Image guided “Standard” SABR (54Gy/3#)
- 5) Quality Assurance measurements
- 6) Quality of Life and Toxicity Assessments

Phase II (n=26)

Adults ≥ 18 years of age
T1N0M0 or T2N0M0 (<4cm) NSCLC; or
A single Metastatic Lung Tumor < 4cm
ECOG performance status 0 to 2
Surgically inoperable
Non-Oxygen dependent at baseline

Calypso Guided Stereotactic Ablative Radiotherapy:

- 1) Endobronchial Calypso Beacon Placement
- 2) 4-Dimensional CT Simulation Scan
- 3) ITV-free and 2mm PTV margin SABR planning
- 4) Respiratory gated Calypso guided SABR (54Gy/3#)
- 5) Quality of Life and Toxicity Assessments
- 6) Radiotherapy dosimetry planning studies

Planned Sample Size: Phase I (n=2); phase II (n=26)

2.0 Background:

Stereotactic Ablative Body Radiotherapy (SABR)

Stereotactic Ablative Body Radiosurgery (SABR) is a modern radiotherapy technique which consists of the delivery of tumoricidal (ablative) doses of radiation to a tumor target inside the body. In contrast to conventional radiotherapy which delivers the total dose to the tumor over six to seven weeks with small daily doses of radiotherapy (2 Gy per fraction for 30 to 33 fractions), SABR is delivered using much larger ablative doses of radiotherapy per fraction (ranging from 8 to 34 Gy per fraction) allowing for the total dose to be delivered in a small number of fractions (1 to 5 fractions). With larger doses per fraction, and delivery of radiotherapy over a shorter period of time, SABR affords a larger biological effective dose of radiotherapy when compared to conventional fractionated radiotherapy. In general, most SABR dose regimens have biological effective doses in excess of 100Gy delivered with conventional fractionation.

To date, SABR has been utilized for the treatment of primary or metastatic tumors of the lung¹, prostate², spine³, liver⁴, and brain⁵ offering excellent local disease control for patients who are either surgically inoperable or for those who refuse surgical management⁶. SABR of early stage non-small cell lung cancers offers local control rates of the target tumor in the range of 90 to 96% at three years following treatment⁷. By contrast, the use of conventional 3-dimensional conformal radiotherapy with doses as high as 70Gy with standard fraction sizes for early stage lung cancer yields considerably inferior results and only provides durable local control in 43% of cases⁸. Thus, from a lung tumor control standpoint for small lung tumors, SABR has become the most widely accepted choice of radiotherapy dose fractionation.

Motion Management Strategies for SABR of Lung Tumors

[figure not shown]
SABR treatment of lung tumors is challenging in that lung tumors are constantly in motion in multiple axes as a result of respiratory and cardiac motion. This motion creates considerable uncertainty in targeting the tumor during SABR treatment. In some cases, small lung tumors can have a respiratory motion path of upwards of 5 centimeters⁹, especially amongst tumors which are located close to the diaphragm in the middle or lower lobes of the lungs¹⁰, or for patients with poor pulmonary function with irregular breathing patterns.

Lung tumor motion has significant implications for radiotherapy treatment planning especially impacting the size of the margin added to the gross tumor volume (GTV) to encompass the moving tumor, and the amount of radiation dose delivered to normal thoracic organs at risk (such as the heart, normal lung tissue, chest wall, ribs, etc). In general, the more a lung tumor moves, the larger the radiotherapy treatment volumes required to encompass the motion and thus the greater the unwanted dose of radiotherapy to healthy OARs (Figure 1).

As such, many strategies have been employed to date in order to manage the motion of lung tumors undergoing SABR treatment including: respiratory gating, breath hold techniques (either deep inspiration, or end-exhalation), abdominal compression plates to force shallow breathing patterns, and motion encompassing strategies (4-Dimensional CT scans). Each of these motion management strategies has their distinct advantages and disadvantages in terms of dosimetric sparing of OARs, patient tolerability/practicality, and accuracy (see table 1).

[figure not shown]
Figure 1: The relationship between tumor motion and radiotherapy field sizes¹¹.

Radiotherapy Field Size

Respiratory gating consists of the delivery of radiation therapy during a pre-selected portion of the respiratory cycle (typically end-exhalation expiration, when the tumor is relatively still) which requires continuous monitoring with an external surrogate marker of breathing motion (such as the Varian RPM system). Respiratory gating (Figure 2) can potentially reduce dose to OARs by reducing the ITV and therefore the PTV volume, however it requires robust correlation of lung tumor motion to the motion of an external surrogate marker. However, this can be difficult for non-compliant patients, or for patients with irregular breathing waveforms. Respiratory gated SABR treatment also takes considerably longer to deliver (since radiotherapy is only delivered during 20 to 30% of each respiratory cycle), especially when using standard radiotherapy dose rates (600 MU/min) which can result in treatment durations as long as 60 minutes per fraction. However, with the advent of rapid radiotherapy dose rates of up to 2400 MU/min attainable using the latest linear accelerator designs (such as the Varian Edge™ at the KIAM) treatment times can be reduced to around 15 to 20 minutes, thus the problem of protracted treatment durations have largely been solved.

[figure not shown]
Figure 2: Respiratory waveform (sinusoidal curve) and gating window during end-exhalation¹².

*Abdominal compression plates*¹³ to induce shallow breathing patterns and *breath-held techniques*¹¹ have the theoretical advantage of reducing dose to OARs by reducing the internal movement of the tumor.

Both methods have been studied extensively, but clinical enthusiasm for their use has largely waned due to concerns of poor tolerability by patients (especially amongst patients with poor pulmonary function and limited respiratory reserve), and the prerequisite of highly compliant and motivated patients.

Figure 3: The end-exhalation breath hold method of lung tumor motion management¹².

The most common forms of lung tumor motion management in clinical use today are motion encompassing methods. These techniques make use of four-dimensional CT simulation scans (*4DCT*) to provide 3D patient anatomy sampled at regular time points throughout the respiratory cycle. A 4DCT is a specialized radiotherapy CT simulation scan whereby the patient is scanned when comfortably free-breathing while their respiratory motion is continuously quantified using an external surrogate marker system (which consists of an infrared marker box placed on the abdominal surface of the supine patient, and its position is monitored continuously).

Both the CT data and the surrogate respiratory motion data are acquired simultaneously during the 4DCT scan which takes approximately 90 seconds to capture¹⁴. Specialized computer software is used to “bin” the scan’s data into ten distinct respiratory-phase correlated CT datasets which represent the different phases of the respiratory cycle. Radiotherapy treatment planning software allows a radiation oncologist to delineate the gross tumor volume (GTV) on each of the ten phases of the respiratory cycle. These 10 GTVs are summed together (using a “merge structure” function) and the resultant structure, termed the internal target volume (ITV)¹⁵ represents all the regions of the lung in which the lung tumor could be at any given moment during the respiratory cycle. The advantage of the ITV based method is that it produces an “individualized” representation of the GTV to account for its internal movement in the body and therefore reduces the possibility of a geographic “miss” of the tumor during SABR. The disadvantage of this method of tumor delineation is that it can make for very large treatment volumes and lead to higher radiation doses to OARs. As a result of the ITV method, a generous portion of a patient’s healthy lung tissues are ablated during SABR and so patients are subject to potential adverse effects due to radiation dose delivered to healthy organs at risk (OAR) nearby to the tumor (summarized in table 2).

Table 1: Overview of Current Lung Tumor Motion Management Strategies

| Management Strategy | Advantages | Disadvantages |
|---|--|--|
| Respiratory Gating | 
 -Potential to reduce OAR dose -No need for traditional ITV -Potential to reduce PTV volume when compared to ITV based approaches | 
 -Protracted Treatment Durations (if using “slow” dose rates) due to low duty cycle (note: this is not an issue with the Varian Edge linear accelerator) -Dependent on external surrogate marker for tumor motion signal -Some patients are unable to breathe with a regular rhythm (anxiety) |
| Abdominal Compression plate | 
 -Reduction in tumor motion due to forced shallow breathing -Reduced internal margin -Potential to reduce PTV volumes when compared to non-compression treatments | 
 -Not well tolerated by patients due to discomfort -Difficult for patients with limited functional lung volumes to tolerate -Time consuming daily treatment setup |
| Motion Encompassing methods (4DCT scans) | 
 -Well tolerated by patients -Can be employed for patients with poor pulmonary function | 
 -Requires use of ITV, which increases treatment volumes (especially for tumors with large motion amplitude). -Dependent on external correlative surrogate for tumor motion |
| Breath hold technique | 
 - Reduced internal margin -No need for ITV -Potential to reduce PTV volumes when compared to non-breath hold techniques -Potential to reduce OAR Dose | 
 -Requires highly compliant patients - Difficult for patients with limited functional lung volumes to tolerate - Dependent on external correlative surrogate for tumor motion |

Table 2: Common Complications to Thoracic Organs At Risk following Standard SABR treatments

| Organ at Risk | Potential Complication | Risk |
|----------------------|-----------------------------------|-------------------------|
| Lung | Pneumonitis (\geq Grade 2) | 10-20% ¹⁶⁻¹⁹ |
| Ribs | Rib Fracture | 35% ²⁰ |
| Chest Wall | Chest Wall Pain (\geq Grade 2) | 39% ²¹ |

Real-time tracking of a lung tumor’s location during SABR treatment would obviate the need to use a standard ITV-based approach for treatment planning and would serve to simultaneously improve the accuracy and precision of SABR while reducing the volume of healthy lung treated to an ablative dose of radiotherapy. Real-time tumor location telemetry data would allow the SABR radiation treatment beam to be automatically activated when the tumor is positioned within the desired target location in the thorax, and deactivated when the tumor moves outside of the chosen target location. This method of radiation treatment delivery is known as respiratory-gated¹² radiotherapy and it carries the potential benefit of reducing the planning target volume of the radiotherapy²². The dosimetric benefits of respiratory-gated radiotherapy depend mainly on the size of the target tumor (larger tumors benefit

more than smaller tumors) and the extent of the motion of the tumor (tumors with large amplitudes benefit the most and tumors with amplitudes <1cm do not seem to benefit in a meaningful way from respiratory gated therapy^{10,23}). Since most patients undergoing SABR treatments are almost always surgically inoperable due to the presence of one or more respiratory comorbidities (emphysema, bronchiectasis, etc) with poor pulmonary function, minimizing the volume of functional normal lung tissue ablated along with the tumor is of critical importance.

SABR Treatment of Lung Tumors using Calypso Tracking Beacons

In 2016, a Varian Edge™ radiotherapy treatment machine (linear accelerator) was installed and commissioned at the Kleysen Institute for Advanced Medicine (KIAM) at the Health Sciences Center (HSC) in Winnipeg, Canada. This state of the art linear accelerator was specifically designed to deliver SABR treatments and is specially equipped with the Calypso™ lung tracking beacon system.

The anchored Calypso™ lung tracking beacon is a grain-of-rice sized transponder beacon (Figure 4) which is placed immediately adjacent to a lung tumor using a flexible bronchoscope. Typically three beacons are placed in the small airways of the lung (2 to 2.5 mm diameter airways) adjacent to the target tumor (within 3 cm of the tumor)²⁴. The Calypso beacon can be used as either a traditional radiopaque fiducial marker (which can be identified using standard kilovoltage x-rays, fluoroscopy, or CT scans) or as a passive electromagnetic beacon transponder. Each beacon measures 2 mm in diameter and 8 mm in length (14mm including the anchoring legs) and consists of a miniature electrical circuit that is encapsulated in a sealed biocompatible glass capsule. In order to prevent the beacon from migrating within the airways, the beacon has an affixed five-legged anchoring system which expands to 5mm in diameter once deployed from the Calypso lung catheter. The Calypso transponder beacon is placed endobronchially using the working channel of a bronchoscope and the Calypso lung catheter (Figure 5). Navigational bronchoscopy can be used to pre-plan the optimal location for each beacon to be placed within the airways by using a pre-bronchoscopy CT scan.

FIGURE 4: The Calypso™ Anchored Transponder Beacon with legs completely constrained (left), and deployed (right).

[figure not shown]
[figure not shown]
[figure not shown]

Figure 5: The single use Calypso Lung Catheter (for use in the working channel of a bronchoscope)

The transponder's electrical circuit is passive and the beacon does not contain an internal energy source. The transponder only emits a radiofrequency (RF) signal when it is excited by a harmless, non-ionizing RF field generated by the Calypso array (Figure 6). After RF excitation, each transponder briefly emits a response signal at a unique frequency that is specific to each beacon. This signal is detected by the sensor array with a refresh rate of 25 times per second (25 Hz). The Calypso system uses this information from all of the beacons to continuously determine the three dimensional location of the tumor isocenter relative to the linear accelerator's isocenter. This allows for real time monitoring of a lung tumor's motion during radiation treatment delivery.

Figure 6: Calypso system components

The Calypso lung beacon was recently granted Health Canada approval for routine endobronchial implantation in human patients following a phase I human study of the Calypso transponder beacon for patients with early stage lung cancer²⁴ which demonstrated excellent tolerability and safety.

In lay terms, the Calypso beacons function similarly to a GPS navigation device, only instead of locating the position of a person on a map, they locate the position of the tumor within the lung in real time at the time of SABR treatment. This real-time tumor position information permits very high accuracy SABR delivery to lung tumors with the potential for significantly smaller treatment volumes and therefore less acute or late SABR related toxicity.

Calypso beacons have been employed in other radiotherapeutic settings including prostate cancer²⁵ and liver cancer. In the case of prostate cancer patients treated with Calypso-guided radiotherapy, the improved accuracy and real-time tumor tracking allowed treatment PTV margins to be reduced to as small as 3mm, which in turn resulted in smaller PTV volumes, less toxicity to nearby organs at risk, and improved quality of life²⁵. It is therefore expected that Calypso-guided radiotherapy could produce analogous beneficial results for patients undergoing SABR treatments for their lung tumors. To this end, we therefore propose this seamless phase I/II prospective clinical trial for patients with mobile tumors of the lungs undergoing SABR which will utilize the Calypso tracking beacon to enable end-exhalation gated, ITV-free radiotherapy treatment planning with minimal PTV margins. The integration of these treatment planning and SABR delivery features is anticipated to reduce radiotherapy treatment volumes, dose to OARs, with excellent tolerability and quality of life.

3.0 Trial Design

This is a prospective, single arm, seamless phase I/II cohort study (investigator initiated trial) with a planned total accrual of 28 patients.

4.0 Study Population:

Potentially eligible patients are adults with surgically inoperable, biopsy proven or suspected single T1N0 or T2N0 Non-small cell lung cancer tumor or patients with a single pulmonary metastasis (<4 cm maximal tumor dimension) from a known primary malignancy of any histology (either metastatic failure to a single pulmonary site after primary radical treatment, or metastatic progression to a single lung metastasis following palliative chemotherapy with no other sites of uncontrolled disease). Tumors should be located either in the lower lobe, lingula, or right middle lobe of the lung however, patients with upper lobe tumors are eligible as long as the tumors have a respiratory amplitude of ≥ 1 cm. Tumors should be located at least 2 cm from the proximal bronchial tree (non-central tumors).

5.0 Eligibility Criteria:

- 1) Adult ≥ 18 years of age who is surgically inoperable, or refusing surgical management.
- 2) Tumor criteria (a patient must satisfy one of “a”, “b” below to be eligible):
 - a. AJCC 7th edition clinical T1aN0M0, T1bN0M0, or T2aN0M0 (<4cm) Non-small cell lung cancer (adenocarcinoma, squamous cell carcinoma, or NSCLC Not Otherwise Specified) of the middle or lower lobes of the lung*;
 - b. A single pulmonary metastasis (<4cm) of a known primary malignancy of any histology involving the middle or lower lobes of the lung* (either metastatic failure to a single pulmonary site after primary radical treatment, metastatic progression to a single lung

[figure not shown]
metastasis following palliative chemotherapy, or a single pulmonary metastatic lesion of newly diagnosed stage IV malignancy).

*upper lobe tumors are eligible for trial participation if the tumor has a demonstrated tumor motion of ≥ 1 cm in any axis (as assessed by fluoroscopy at the time of bronchoscopy).

- 3) Confirmation of malignancy (a patient must satisfy one of “a”, “b” below to be eligible):
 - a. Tumors accessible by bronchoscopy, image-guided percutaneous biopsy, or other invasive staging methods require biopsy confirmation of malignancy.
 - b. If a tumor is not amenable to a diagnostic biopsy, evidence of growth of the target tumor on serial imaging scans is necessary prior to enrollment. An increase in SUV of the target tumor on serial PET scans is also acceptable.
- 4) ECOG performance status of 0 to 2.
- 5) Minimum life expectancy of 6 months.
- 6) Deemed fit to undergo bronchoscopy by their participating thoracic surgeon
- 7) Deemed fit to undergo SABR by their participating Radiation Oncologist.
- 8) Respiratory function (a patient must satisfy both “a” and “b” below):
 - a. Minimum FEV1 of 0.8 liters
 - b. Minimum DLCO of 35% predicted.
- 9) Able to provide written informed consent and understand verbal instructions necessary for radiotherapy treatments.

Exclusion Criteria:

- 1) Tumors located < 1 cm from the chest wall based on CT imaging.
- 2) Tumors located ≤ 2 cm from the proximal bronchial tree (see figure 7)
- 3) Patients who require supplemental oxygen at rest.
- 4) Patients who are unable to lie flat or still for a minimum of 30 minutes.
- 5) ECOG performance status 3 or 4.
- 6) Evidence of uncontrolled extra-thoracic metastatic disease (based on imaging or clinical findings).
- 7) Proven or suspected intrathoracic lymph node involvement.
- 8) Prior SABR to the target tumor.
- 9) Prior history of idiopathic pulmonary fibrosis, interstitial lung disease, or active collagen vascular disease (systemic lupus erythematosus, Rheumatoid arthritis, or Scleroderma)
- 10) Pregnancy.
- 11) Active pulmonary infection
- 12) Known hypersensitivity to nickel titanium (Nitinol)
- 13) Known Bronchiectasis of the small airways nearest to the tumor

Figure 7: The proximal bronchial tree (tumours within this region are ineligible for trial participation).**6.0 Study Objectives:****Phase I:**

- 1) To allow for members of the interdisciplinary care team (Thoracic surgeons, Radiation Oncology, Radiation Therapists, and Medical Physicists) to familiarize themselves with the clinical use of implanted endobronchial tumor tracking beacons and carry out quality assurance assessments in preparation for the subsequent phase II component of the study.
- 2) To quantify the presence (if any) of beacon migration (inter-beacon distance) at different time points in a patient's care path (time of implantation, CT simulation scan, and days of SABR treatment).
- 3) To assess the quality of life of patients having Calypso placement (EORTC QLQ - LC13 questionnaire)
- 4) To assess acute toxicity of beacon implantation using the Common Terminology for Criteria for Adverse Events (CTCAE version 4.0)
- 5) To quantify the potential benefit of continuous monitoring of tumor location using Calypso by comparing it to traditional imaging-based setup.

Phase II:

- 1) To quantitatively assess the differences in irradiated treatment volumes and radiotherapy dose volume metrics for the PTV and healthy thoracic organs at risk between Calypso™ guided respiratory gated SABR and the traditional ITV based radiotherapy.
- 2) To serially quantify the acute and late toxicity of patients undergoing Calypso™ guided SABR using the Common Terminology Criteria for Adverse Events (CTCAE) Version 4.0
- 3) To serially quantify the self-reported quality of life of patients undergoing Calypso Guided SABR using the EORTC QLQ - LC13 questionnaire
- 4) To serially biobank blood and urine samples for patients undergoing radical SABR of lung tumors to allow for the future development of novel prognostic and predictive biomarkers for patients undergoing SABR.
- 5) To serially quantify changes to pulmonary function following SABR treatment

- 6) To demonstrate the benefit of Calypso treatments in reducing patient-specific component of PTV margins

Study Hypotheses:

Phase I: Calypso beacon placement will be safe and well tolerated and will function within their specified tolerances with minimal (sub-millimeter) inter-beacon migration.

Phase II: The Median Planning Target Volume (PTV) of Calypso guided respiratory gated SABR will be 40% smaller than the median PTV volume of standard ITV based SABR treatment with standard PTV margins. Furthermore, thoracic organs at risk will receive significantly less radiotherapy dose when compared to the standard SABR treatment.

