Percentage Change in Organ at Risk Dose Volume Metrics: For each organ at risk, percentage change in the dose-volume histogram metric of interest will be calculated as per the following example:

$$\% \text{ Change in Lung V20} = (\text{V20}_{\text{standard SABR}} - \text{V20}_{\text{Calypso Guided SABR}}) / \text{V20}_{\text{standard SABR}} \times 100$$

Pulmonary Function Test Results: Percentage change in pulmonary function test results (FEV1, DLCO, and 6 minute walk distance) will be calculated as per the following example at each follow-up time point:

$$\% \text{ Change FEV1} = (\text{FEV1}_{\text{baseline}} - \text{FEV1}_{\text{follow-up}}) / \text{FEV1}_{\text{baseline}} \times 100\%$$

Local Control: The RECIST³⁰ version 1.1 criteria will be used to assess the effect of SABR treatment on the local control of the tumor as per the following definitions:

| RECIST Outcome | Description |
|--------------------------|--|
| Complete Response (CR) | Disappearance of all target lesions |
| Partial Response (PR) | At least a 30% decrease in the sum of the LD of target lesions, taking as reference the baseline sum LD |
| Progressive Disease (PD) | At least a 20% increase in the sum of the LD of target lesions taking as reference the smallest sum LD recorded since the treatment started or |

| | |
|----------------------|---|
| | the appearance of one or more new lesions |
| Stable Disease (SD): | Neither sufficient shrinkage to qualify for PR nor sufficient increase to qualify for PD, taking as reference the smallest sum LD since the treatment started |

- 7) Survival: Progression-Free Survival (PFS), Cancer-Specific Survival (CSS), and Overall Survival (OS) will be estimated using the Kaplan-Meier method. For all three survival estimates, the survival period will be defined as the time from tissue diagnosis to progression event (for PFS), Cancer related death (CSS), death from any cause (OS) or time of censoring (due to loss to follow-up, or end of study).

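### The schema and Section 4 define a different cohort from the Section 5 criteria, and PFS, CSS and OS are then estimated without a split by disease setting

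*Combined protocol and SAP*

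**What the plan says.** On operability, the schema (Section 1) lists "Surgically inoperable" for both phases, whatever the disease type. Section 4 opens with "Potentially eligible patients are adults with surgically inoperable, biopsy proven or suspected single T1N0 or T2N0 Non-small cell lung cancer tumor" and then adds patients with a single pulmonary metastasis. Criterion 1 in Section 5 reads "Adult ≥ 18 years of age who is surgically inoperable, or refusing surgical management".

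On metastatic disease, Section 4 lists two settings as alternatives. One is failure at a single lung site after radical treatment of the primary. The other is "metastatic progression to a single lung metastasis following palliative chemotherapy with no other sites of uncontrolled disease". Criterion 2b repeats both, leaves out the closing condition of the second, and adds a third setting: "or a single pulmonary metastatic lesion of newly diagnosed stage IV malignancy". The only exclusion directed at other uncontrolled disease is exclusion 6: "Evidence of uncontrolled extra-thoracic metastatic disease (based on imaging or clinical findings". Exclusion 7 separately removes intrathoracic nodal involvement.

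On analysis, Section 7 lists PFS, CSS and OS as secondary endpoints 6 to 8. Section 13 states that "Progression-Free Survival (PFS), Cancer-Specific Survival (CSS), and Overall Survival (OS) will be estimated using the Kaplan-Meier method", with time running from tissue diagnosis. It gives no strata, subgroups or hypothesis test for them.

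**The concern.** A single-arm trial of 28 patients has no control group to absorb differences in case mix, so the description of who was enrolled carries the interpretation. Here an investigator who follows the numbered criteria can enrol patients whom Section 4 or the schema leaves out.

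Some of these patients may have an untreated or uncontrolled primary. Progression or cancer death in such a patient may have nothing to do with SABR to the lung target, yet it counts in the same PFS and CSS estimates as an event in a patient with T1 or T2 N0 NSCLC. The baseline table in Section 13 would not reveal the mix. It has rows for T-stage, size, lobe and histology, but none for primary versus metastasis, for metastatic setting, or for inoperable versus refusing surgery.

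**Working it through.** **The plan's own figure.** The documents give no event rate, precision target or power for PFS, CSS or OS. The one power statement concerns PTV (Section 13): 28 patients, 40% reduction from 62.9 cm³, SD 43.6 cm³, one-sided alpha 0.05, power 0.92. Treating 43.6 as the SD of the within-patient difference:

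- difference = 0.40 × 62.9 = 25.16 cm³
- standard error = 43.6 / √28 = 8.24
- power = Φ(25.16 / 8.24 − 1.645) = Φ(1.41) = 0.92

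This reproduces. Reconciling the eligibility text changes none of these inputs. Both PTVs come from the same patient's 4DCT, so the comparison does not depend on prognosis.

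**The eligibility texts side by side.** Each row is a patient who meets the other requirements.

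| Patient | Schema | Section 4 | Section 5 |
|---|---|---|---|
| NSCLC, operable, refuses surgery | out | out | in (criterion 1) |
| Metastasis, operable, refuses surgery | out | not stated | in (criterion 1) |
| Inoperable, newly diagnosed stage IV, one lung lesion | in (setting not specified) | out | in (criterion 2b) |
| Inoperable, progression after chemotherapy, primary uncontrolled | not addressed | out | not excluded on this point |

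Two entries need care. In Section 4 the inoperability wording grammatically governs the NSCLC patients, so for metastasis patients who refuse surgery the conflict is with the schema alone. The Section 4 condition on uncontrolled disease may attach only to the post-chemotherapy setting. Even on that narrow reading, criterion 2b repeats the setting without the condition.

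**What the exclusions reach.** Criterion 2b requires a single lung metastasis, so further lung metastases fail. Exclusion 6 removes uncontrolled metastases outside the thorax, and exclusion 7 removes nodal disease. A primary tumour is not a metastasis, so an uncontrolled node-negative primary is caught by neither exclusion. The same holds for other uncontrolled thoracic disease that is neither nodal nor a lung metastasis.

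**What pooling does.** Let p be the share of criterion 2a patients, and S2a(t) and S2b(t) the survival functions of the two groups. Without censoring, the pooled curve estimates

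S(t) = p × S2a(t) + (1 − p) × S2b(t).

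If p moves from p1 to p2, S(t) moves by (p2 − p1) × [S2a(t) − S2b(t)]. The pooled result is free of the mix only if the two groups have the same survival, which cannot be presumed for T1 or T2 N0 NSCLC and metastatic disease of any histology. The documents give no value for p, S2a or S2b, so the shift has no computable size.

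The formula also shows what reconciliation alone would achieve. Section 4 already combines early-stage NSCLC with metastases, so p lies between 0 and 1 under either text. Aligning the criteria settles who is enrolled. Only separate reporting deals with the mixing.

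**The case against.** The best defence is that Section 5 governs enrolment and Section 4 merely summarises it, since it speaks of patients who are potentially eligible. The Background (Section 2) describes SABR as an option for inoperable patients and for those who refuse surgery, so criterion 1 fits the protocol's stated use, and the schema entry could be shorthand. Exclusions 6 and 7, a minimum life expectancy of 6 months, and the fitness judgements by both specialists narrow the remaining gap. Survival is not among the listed objectives, and splitting 28 patients costs precision.

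Much of this stands. It answers anyone who might infer that the pooled survival curves describe no defined group: the numbered criteria do define one, though not the one in Section 4 and the schema. It does not remove the contradiction, because nothing in the protocol says which section prevails, and Section 4 presents its two metastatic settings as a closed pair of alternatives.

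A reader might also infer that mixed survival estimates would distort the planning of phase III. The documents do not support this. The schema assigns that role to quality of life and toxicity, not to survival.

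**Conclusion.** The contradictions are confirmed from the text. The schema and Section 4 differ from Section 5 on surgery refusers, Section 4 differs from Section 5 on newly diagnosed stage IV and on control of disease elsewhere, and exclusion 6 does not reach an uncontrolled primary. Combined with unsplit Kaplan-Meier estimates, this leaves PFS, CSS and OS dependent on the enrolled mix of early-stage NSCLC and metastatic patients. That conclusion assumes only that the two groups do not share the same survival. The consequence is confined to descriptive secondary endpoints; the primary PTV endpoint and its power are unaffected.

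No magnitude can be given. It is tempting to assume a number of newly diagnosed stage IV patients who all progress early and to read off a fall in 12-month PFS. Such a figure would rest entirely on the assumed mix, and the plan's clock starts at tissue diagnosis rather than at SABR. A reader might also suppose that surgery refusers would raise OS and offset the effect; nothing in the documents gives their survival or supports a direction.

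**What to change.** The sponsor should reconcile the schema, Section 4, criteria 1 and 2b and exclusion 6 so that they state one population. The text should say explicitly how patients refusing surgery, newly diagnosed stage IV disease and an uncontrolled primary are handled. Which rule is right is the sponsor's decision.

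Add baseline rows for disease setting (criterion 2a, and each metastatic setting under 2b) and for operability (inoperable or refusing surgery).

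Report PFS, CSS and OS separately for criterion 2a and criterion 2b patients, and label any pooled curve as descriptive.

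The cost is a wording amendment to Sections 1, 4 and 5, a few table rows and one split of the survival output. The downside is smaller groups and wider intervals. As an illustration, if the 28 patients divided evenly, each group would have 14, and at the same underlying survival each standard error would be about √(28/14) = 1.4 times that of the pooled curve. The sample size and the primary analysis need no change.
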